6.3 Monitoring and Toxicity Management

Each patient receiving ibrutinib will be evaluated for safety. The safety parameters include all laboratory tests and hematological abnormalities, physical findings, and spontaneous reports of adverse events reported to the investigator by patients.

We will monitor for potential adverse effects including but not limited to fatigue, dehydration, cytopenias, leukocytosis, diarrhea, nausea, vomiting, signs and symptoms of infection including pneumonia, as well as skin disorders including rash.

Acute toxicity will be managed by supportive care and/or delay of dose. Further management will depend upon the judgment of the treating clinician and may include dose reduction. Guidelines for dose modification and management of anticipated adverse events are summarized in Table 5.3.1.

Criteria for dose adjustments and management of ibrutinib related toxicities

Toxicity and Intensity	Dose Modification and Suggestions for Management
Fatigue (very common)	
Grade 1 (relieved by rest)	Ensure adequate caloric intake and assess volume status. Rule out other causes of fatigue including anemia. Avoid prescription of steroids (e.g., Prednisone or Dexamethasone) which has immunomodulatory effects and may affect study endpoints.
Grade 2 (not relieved by rest, limiting instrumental ADL)	Ensure adequate caloric intake and assess volume status. Rule out other causes of fatigue including anemia. Avoid prescription of steroids (e.g., Prednisone or Dexamethasone) which has immunomodulatory effects and may affect study endpoints. If fatigue is not resolved to \leq grade 1 with supportive management, reduce the starting dose of ibrutinib by 140mg.
Grade 3 (not relieved by rest, limiting self care ADL)	Ensure adequate caloric intake and assess volume status. Rule out other causes of fatigue including anemia. Avoid prescription of steroids (e.g., Prednisone or Dexamethasone) which has immunomodulatory effects and may affect study endpoints. Hold ibrutinib dosing until fatigue is resolved to \leq grade 2, at which time restart dose at 50% of the starting dose.
Diarrhea (very common)	
Grade 1 (increase of <4 stools per day over baseline)	Consider Clostridium difficile testing if clinically indicated. The patient should be monitored carefully to ensure maintenance of fluid intake to avoid dehydration. Manage with supportive therapy including antidiarrheals.
Grade 2 (increase of 4-6 stools per day over baseline)	Patient should be evaluated by the treating clinician or other physicians including history and physical exam. Infectious work-up include Clostridium difficile and other suspected organisms should be obtained. The patient should be monitored carefully to ensure maintenance of fluid intake to avoid dehydration. If infectious work-up is negative, patient should be managed with supportive therapy including antidiarrheals. If symptoms are prolonged (e.g., >2 weeks) and do not improve with supportive management, reduce the starting dose of ibrutinib by 140mg.
Grade 3 (increase of \geq 7 stools per day over baseline; incontinence; hospitalization indicated)	Hospitalization with management per standard institutional practices. Rule out Clostridium difficile . Hold ibrutinib until diarrhea \leq grade 1, then resume ibrutinib at 50% of the starting dose.
Grade 4 (Life-threatening consequences; urgent intervention indicated)	Urgent hospitalization and medical management per standard institutional practices. Discontinue ibrutinib therapy.
Nausea/Vomiting (very common)	
Grade 1 (loss of appetite without alteration in eating habits; 1-2 episodes of vomiting in 24 hours)	5-HT3 antagonists (e.g., Ondansetron), D2 antagonists (e.g., Prochlorperazine), or other antiemetic, alone or in combination can prevent nausea in the majority of patients. Avoid prescription of steroids (e.g., Prednisone or Dexamethasone) which has

Toxicity and Intensity	Dose Modification and Suggestions for Management
	immunomodulatory effects and may affect study endpoints.
Grade 2 (oral intake decreased without significant weight loss, dehydration or malnutrition; 3-5 episodes of vomiting in 24 hours)	Implement one or more combinations of antiemetics. Avoid prescription of steroids (e.g., Prednisone or Dexamethasone) which has immunomodulatory effects and may affect study endpoints.
Grade 3 (inadequate oral caloric or fluid intake; tube feeding, TPN or hospitalization indicated; ≥ 6 episodes of vomiting in 24 hours)	Hospitalization and supportive management including hydration and caloric intake per standard institutional practices. Hold ibrutinib until nausea \leq grade 1, then resume ibrutinib at 50% of the starting dose after adequate fluid and caloric intake are achieved. Avoid steroids (e.g., Prednisone or Dexamethasone) which has immunomodulatory effects and may affect study endpoints.
Cough (very common)	
Grade 1 (mild symptoms, nonprescription intervention indicated)	Symptomatic management with OTC cough suppressants (e.g., Robitussin).
Grade 2 (moderate symptoms, medical intervention indicated; limiting instrumental ADL)	Chest imaging as clinically indicated to rule out pneumonia. Trial of prescription cough suppressants (e.g., Benzonatate). If symptoms are prolonged (e.g., >2 weeks) and do not improve, reduce the starting dose of ibrutinib by 140mg.
Grade 3 (severe symptoms; limiting self care ADL)	Chest imaging as clinically indicated to rule out pneumonia. Hospitalization if clinically indicated. Hold ibrutinib until cough \leq grade 1, and any reversible causes (e.g., pneumonia) are fully treated. Then resume ibrutinib at 50% of the starting dose.
Pneumonia (very common)	
Grade 2 (moderate symptoms; oral intervention indicated)	Oral antibiotic, antifungal or antiviral as clinically indicated. Chest imaging if clinically indicated. If symptoms are prolonged (e.g., >2 weeks) and do not improve, reduce ibrutinib starting dose by 140mg.
Grade 3 (IV intervention indicated; radiologic, endoscopic or operative intervention indicated)	Hospitalization for infectious work-up and management including imaging and endoscopic or operative intervention per standard institutional practices. IV antibiotic, antifungal and/or antiviral per standard institutional practices. Hold ibrutinib until pneumonia is fully treated, then resume at 50% of the starting dose.
Grade 4 (life-threatening consequences; urgent intervention indicated)	Hospitalization and management including IV antibiotics, antifungal and/or antiviral per standard institutional practices. Discontinue ibrutinib.
Maculopapular rash (very common)	
Grade 1 (<10% BSA covered with or without symptoms)	Continue dose level of ibrutinib. Review medications for other potential drug etiologies and discontinue agent(s) as appropriate. Use topical or oral antihistamines for symptomatic relief. Topical corticosteroids may be used if clinically indicated. Avoid systemic corticosteroids which has systemic immunomodulatory effects and may affect study endpoints.
Grade 2 (10-30% BSA covered with or without symptoms; limiting instrumental ADL)	Review medications for other potential drug etiologies and discontinue suspected agent(s) as appropriate. Use topical or oral antihistamines for symptomatic relief. Topical corticosteroids may be used if clinically indicated. Avoid systemic corticosteroids which has systemic immunomodulatory effects and may affect study endpoints. If symptoms are prolonged (e.g., >2 weeks) and do not improve, reduce the starting dose of ibrutinib by 140mg.

Toxicity and Intensity	Dose Modification and Suggestions for Management
Grade 3 (>30% BSA covered with or without symptoms; limiting self care ADL)	Review medications for other potential drug etiologies and discontinue suspected agent(s) as appropriate. Use topical or oral antihistamines for symptomatic relief. Topical corticosteroids may be used if clinically indicated. Avoid systemic corticosteroids which has systemic immunomodulatory effects and may affect study endpoints. Hold ibrutinib until rash \leq grade 1, and then resume at 50% of the starting dose.
Anemia (very common)	
Grade 1 (Hb <LLN-10.0 g/dL)	Maintain ibrutinib dose level. Assess for evidence of gastrointestinal bleeding.
Grade 2 (Hb <10.0-8.0 g/dL)	Assess for evidence of gastrointestinal bleeding. Hold ibrutinib until anemia is resolved to \leq grade 1, at which time resume ibrutinib at 140mg lower than the starting dose.
Grade 3 (Hb <8.0 g/dL, transfusion indicated)	Transfuse PRBC per standard institutional practices. Hold ibrutinib until anemia \leq grade 1, and then resume at 50% of the starting dose. Red blood cell growth factors (erythropoietin) are permitted per institutional policy and in accordance with the ASCO guidelines. Short doses of steroids for autoimmune cytopenias are permitted for <14 days at doses that do not exceed 100 mg per day of prednisone or equivalent.
Thrombocytopenia (very common)	
Grade 1 (Plt <LLN- 75,000/mm ³)	Check manual blood smear to rule out pseudothrombocytopenia. Maintain ibrutinib dose level.
Grade 2 (Plt <75,000-50,000/mm ³)	Check manual blood smear to rule out pseudothrombocytopenia. Hold ibrutinib until thrombocytopenia is resolved to \leq grade 1, at which time resume at 140mg lower than the starting dose.
Grade 3 (Plt <50,000-25,000/mm ³)	Check manual blood smear to rule out pseudothrombocytopenia. Hold ibrutinib until thrombocytopenia \leq grade 1, and then resume at 50% of the starting dose. Platelet transfusions may be given if clinically indicated (e.g., bleeding).
Grade 4 (Plt <25,000/mm ³)	Check manual blood smear to rule out pseudothrombocytopenia. Discontinue ibrutinib. Platelet transfusions may be given if clinically indicated (e.g., bleeding or Plt <10,000/mm ³). Short courses of steroids for autoimmune cytopenias are permitted for <14 days at doses that do not exceed 100mg per day of prednisone or equivalent.
Neutropenia (very common)	
Grade 1 (ANC <LLN-1,500/mm ³)	Maintain ibrutinib dose level. Avoid the use of growth factors due to potential interference with immune effects of ibrutinib and study endpoints.
Grade 2 (ANC <1,500-1,000/mm ³)	Hold ibrutinib until neutropenia is resolved to \leq grade 1, at which time resume at 140mg lower than the starting dose. Avoid the use of growth factors due to potential interference with immune effects of ibrutinib and study endpoints.
Grade 3 (ANC <1000-500/mm ³)	Hold ibrutinib until neutropenia is resolved to \leq grade 1, at which time resume at 50% of the starting dose. Avoid the use of growth factors due to potential interference with immune effects of ibrutinib and study endpoints.
Grade 4 (ANC <500/mm ³)	Discontinue ibrutinib. Growth factors such as filgrastim or

Toxicity and Intensity	Dose Modification and Suggestions for Management
	pegfilgrastim may be used per institutional policy and in accordance with the ASCO guidelines.
Febrile neutropenia (common)	
Grade 3 (ANC <1000/mm ³ with a single temp >38.3°C (101 F) or a sustained temp of ≥38°C (100.4 F) for >1 hour	Urgent admission and management including IV antibiotics per standard institutional practices. Hold ibrutinib until neutropenia is resolved to ≤ grade 1 and any evident infection is adequately treated, then resume ibrutinib at 140mg lower than the starting dose. Avoid the use of growth factors due to potential interference with immune effects of ibrutinib and study endpoints.
Grade 4 (life-threatening consequences; urgent intervention indicated)	Discontinue ibrutinib. Urgent admission and management including IV antibiotics per standard institutional practices. Growth factors may be used if clinically indicated.
Leukocytosis (common)	
Grade 3 (ANC >100,000/mm ³)	Admit patient for close monitoring including CBC and signs and symptoms of leukostasis. Hold ibrutinib until ANC normalizes, at which time resume ibrutinib at 50% of the starting dose.
Grade 4 (clinical manifestations of leukostasis; urgent intervention indicated)	Discontinue ibrutinib. Supportive care including hydration and/or cytoreduction per standard institutional practices.
Other ibrutinib-related AEs	
Grade 1 or 2	Maintain dose level and initiate standard supportive care. If grade 2 toxicity does not improve to ≤ grade 1 with optimal supportive care, reduce ibrutinib dose by 140mg.
Grade 3	Hold ibrutinib until resolve to ≤ grade 1, then reduce dose by 50%.
Grade 4	Discontinue ibrutinib.
Frequency category is based on the following:	

 Very common: anticipated ≥10% Common: anticipated ≥1% and <10% 	
Notes:	

 All dose modifications should be based on the worst preceding toxicity. If a patient requires a dose interruption of >14 days due to a study drug related toxicity, the patient must be discontinued from the study. Patients who discontinue the study for a study related AE must be followed at least once a week for 28 days and subsequently at 28 day intervals until resolution or stabilization of the event, whichever comes first. 	

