6.1.4 Dose Limiting Toxicities

Each patient in the safety lead-in will be assessed periodically for the development of any toxicity as outlined in Section 7 Study Procedures and Observations. Toxicity will be assessed according to the NCI CTCAE v4.0. Dose adjustments will be made according to the system showing the greatest degree of toxicity.

Dose de-escalation in this study will be based on the occurrence of dose-limiting toxicities (DLTs) that occur during the duration of ibrutinib therapy and the period after the last dose of ibrutinib until the day of surgery. DLTs will be defined as any of the following that are attributable to ibrutinib.

- Any grade 4 toxicity, including hematologic toxicities with the exception of lymphocytosis. Lymphocytosis, in the absence of clinical symptoms, is excluded from DLT, as this may be considered an on-target pharmacodynamics effect of BTK inhibition.
- Any grade 3 toxicity.
- Any recurrence of the same grade 3 toxicity.
- Any delay of RP due to study-drug related toxicity.
- Any complications of RP (e.g., bleeding, delayed wound healing) deemed to be related to study drug.

The dose of study drug should be modified according to the dose modification guidelines, including any of the following toxicities:

- Grade 4 ANC (<500/mm³) for more than 7 days.
- Grade 3 thrombocytopenia (<50,000/mm³) in the presence of clinically significant bleeding events.
- Grade 4 thrombocytopenia (<25,000/mm³).
- Grade 3 or 4 nausea, vomiting, or diarrhea if persistent, despite optimal anti-emetic and/or anti-diarrheal therapy.

Patients who experience a DLT may be removed from protocol therapy and undergo RP at the discretion of the operating surgeon.

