6.2 Dose Modifications for an Individual Patient Regardless of Dose Cohort

If a patient experiences any CTCAE v4.0 grade 4 toxicity attributed to treatment, ibrutinib must be discontinued. If a patient experiences any CTCAE v4.0 grade 3 toxicity attributed to treatment, ibrutinib must be held until resolution of the toxicity to grade 1 or the patient's baseline, at which time the patient may resume ibrutinib at 50% of the starting dose. If the patient experiences recurrence of the same grade 3 toxicity while on 50% reduced dose,

ibrutinib must be discontinued. If a grade 3 toxicity does not resolve to grade 1 or the patient's baseline within 2 weeks of holding therapy, ibrutinib must be discontinued.

Ibrutinib Dose Modifications According to Toxicity

Event	Management
Any grade 4 toxicity attributed to treatment	Discontinue ibrutinib
Any grade 3 toxicity attributed to treatment	Hold ibrutinib until \leq grade 1, then resume ibrutinib at 50% starting dose
Recurrence of the same grade 3 toxicity while on half dose	Discontinue ibrutinib
Grade 3 toxicity not resolving to \leq grade 1 within 2 weeks	Discontinue ibrutinib

Clinical judgment of the treating physician should guide the management plan of each patient based on individual benefit/risk assessments.

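### The Section 6.3 row for grade 3 febrile neutropenia restarts ibrutinib at 700 mg, where Section 6.2 and the overlapping grade 3 neutropenia row give 420 mg

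*Combined protocol and SAP*

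**What the plan says.** Section 6.2 gives the general rule for an individual patient. When a grade 3 event is judged to be caused by the drug, dosing stops until the event has recovered to grade 1 or to the level the patient had at entry. On the dose after recovery, the section reads "at which time the patient may resume ibrutinib at 50% of the starting dose". The short table in Section 6.2 repeats the 50% step.

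The table in Section 6.3 then goes event by event. Its grade 3 neutropenia row holds the drug until neutropenia is grade 1 or lower, "at which time resume at 50% of the starting dose". Its grade 3 febrile neutropenia row (neutrophils below 1,000/mm³ with fever) requires urgent admission and intravenous antibiotics. It holds the drug until counts recover and any infection is treated, "then resume ibrutinib at 140mg lower than the starting dose".

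Two general statements bear on overlapping events. A note under the Section 6.3 table says "All dose modifications should be based on the worst preceding toxicity". Section 6.1.4 says "Dose adjustments will be made according to the system showing the greatest degree of toxicity". Nothing in the document exempts febrile neutropenia from Section 6.2 or states which section prevails.

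**The concern.** The protocol gives two restart doses for one event. Section 6.2 conflicts with the febrile neutropenia row, and the Section 6.3 table conflicts with itself, because the neutrophil criterion for that row places the patient in a neutropenia row as well. The difference also runs against clinical sense: the patient with fever, admission and intravenous antibiotics gets a smaller reduction than the afebrile patient with the same count.

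What is at stake is the dose a patient takes after a serious infection-risk event in the weeks before a prostatectomy. Two investigators, each able to point to protocol text, could prescribe 700 mg and 420 mg for the same event. Consistency of treatment within the cohort is a secondary issue.

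**Working it through.** The plan states no figure to reproduce. The check is dose arithmetic followed by a comparison of rows.

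**Inputs.** Starting dose 840 mg daily for 28 days (Sections 6.1 and 6.1.2). Level -1 is also 840 mg daily; Level -2 is 560 mg daily (Section 3.1). Restart at 50% of the starting dose (Section 6.2 and the grade 3 neutropenia row) or at the starting dose minus 140 mg (grade 3 febrile neutropenia row).

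**Restart dose.**

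| Starting dose | Febrile neutropenia row | Section 6.2 and neutropenia row | Difference | Ratio |
|---|---|---|---|---|
| 840 mg | 840 − 140 = 700 mg (700/840 = 83.3%) | 0.5 × 840 = 420 mg | 280 mg/day | 700/420 = 1.67 |
| 560 mg | 560 − 140 = 420 mg (420/560 = 75%) | 0.5 × 560 = 280 mg | 140 mg/day | 420/280 = 1.5 |

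The planned course is 28 × 840 = 23,520 mg, so at an 840 mg start each dose after restart adds 280/23,520 = 1.2% of the planned total. The documents do not give the timing of onset. If 7 to 14 doses remained, which is an assumption for illustration only, the excess would be 7 × 280 = 1,960 mg to 14 × 280 = 3,920 mg, or 8.3% to 16.7%.

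**Row count.** The Section 6.3 table has 12 grade 3 rows: fatigue, diarrhea, nausea/vomiting, cough, pneumonia, rash, anemia, thrombocytopenia, neutropenia, febrile neutropenia, leukocytosis and other events. Eleven use the 50% step; only febrile neutropenia does not. Elsewhere in the table the 140 mg step appears only in grade 2 rows (fatigue, diarrhea, cough, pneumonia, rash, anemia, thrombocytopenia, neutropenia, other). Grade 3 pneumonia, also managed with intravenous therapy, restarts at 50%. This pattern suggests a drafting slip more than a deliberate exception, though the document does not say.

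**Overlap by neutrophil count, with fever.**
- From 500 to below 1,000/mm³: the grade 3 neutropenia row (50%) and the grade 3 febrile neutropenia row (minus 140 mg) both apply. The two general statements rank by severity. Both rows are grade 3, so neither statement decides between them.
- Below 500/mm³: the grade 4 neutropenia row requires discontinuation. Here the worst-toxicity note does decide, and the drug stops.

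**Fatigue row.** Grade 3 fatigue may restart at grade 2 or lower, while Section 6.2 requires grade 1 or baseline. The restart dose is 50% in both, so this mismatch is minor.

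**The case against.** The strongest reply is that the Section 6.3 table is guidance. Its column heading covers suggestions for management, its introduction leaves further management to the treating clinician, and Section 6.2 ends with a clinical-judgment clause. Section 6.2 is also permissive about restarting at all, and in the lead-in a patient with a dose-limiting toxicity may be taken off therapy. A site that follows Section 6.2 would find no authority there for 700 mg. All of this is fair, and it means that 700 mg is a possible outcome and not a required one. It does not remove the conflict: Section 6.1.4 says doses should be modified according to the guidelines, the guidelines give two doses, and no discretionary wording names a different dose for febrile neutropenia.

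A reader might also infer that the row delays mandatory discontinuation, since Section 6.2 ties it to "recurrence of the same grade 3 toxicity while on 50% reduced dose": a patient restarted at 700 mg would seem to be allowed a third episode. The documents do not support this. It requires the Section 6.3 row to govern the first event and Section 6.2 the second. If Section 6.2 governs throughout, discontinuation comes at the second event. If the row governs throughout, a recurrence leads to 700 mg again. The path is also barely reachable: it needs three episodes and two holds within Days 1 to 28, and an interruption of more than 14 days ends participation.

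A general rule that the stricter instruction always governs may look like the natural repair. It would do harm. The text of Section 6.2 allows restart at the patient's baseline, whereas most rows require grade 1 or lower. The inclusion criteria accept hemoglobin above 9, and the table's grade 2 anemia runs from 8.0 to below 10.0 g/dL. A patient enrolled at 9.5 could return to baseline after grade 3 anemia and restart under Section 6.2, but not under a stricter-governs rule.

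**Conclusion.** The inconsistency is real and worth correcting. For grade 3 febrile neutropenia with neutrophils from 500 to below 1,000/mm³, the protocol gives restart doses of 700 mg and 420 mg at an 840 mg start, and 420 mg and 280 mg at Level -2, with no rule to choose between them. The conclusion rests on the event being attributed to ibrutinib and on the investigator choosing to restart.

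The practical reach is small. The table labels febrile neutropenia as anticipated in at least 1% and under 10% of patients, but that label is not split by grade. The pooled safety data come mainly from B-cell malignancy patients treated for longer, so no case count can be given with confidence; few patients are likely to be affected.

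A reader might expect the safety rules or the sample size to be compromised. They are not. An attributed grade 3 event in the lead-in already counts as a dose-limiting toxicity, and a treatment-related grade 3 event already counts in the 10-patient review, whatever the restart dose. The power calculation does not use the restart dose.

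**What to change.** In the Section 6.3 table, change the end of the grade 3 febrile neutropenia row so that ibrutinib resumes at 50% of the starting dose, matching Section 6.2 and the grade 3 neutropenia row. Keep the existing conditions on count recovery and treatment of infection. As a minor companion edit, change the restart criterion in the grade 3 fatigue row to grade 1 or the patient's baseline. Do not add a general precedence sentence; with these two rows corrected, this point does not need one.

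The cost is the wording of two table rows, carried in a protocol amendment. Sample size, visits and analyses do not change. If the sponsor does intend a smaller reduction for febrile neutropenia, the alternative is to say so in Section 6.2 as a named exception, give the reason, and state that it overrides the neutropenia row.

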Unique Aspects of this Study	
This is the first study to evaluate the safety of ibrutinib and its effect on B cell infiltration in the neoadjuvant setting for patients with localized prostate cancer. The secondary and exploratory objectives will enhance our understanding of the immunomodulatory and cytotoxic effects of Btk inhibition in prostate cancer. Findings may justify further exploration of ibrutinib in prostate cancer, including combinational therapy in advanced prostate cancer.

List of Abbreviations

5-HT	5-hydroxytryptamine (serotonin)
ADL	activity of daily living
ADT	androgen deprivation therapy
AE	adverse event
ALP	alkaline phosphatase
ALT	alanine aminotransferase
ANC	absolute neutrophil count
AST	aspartate aminotransferase
ATC	Anatomical Therapeutic Chemical (Classification System)
AUC	area under the curve
B-CLL	B-cell chronic lymphocytic leukemia
BCR	B-cell receptor
Breg	B regulatory cells
BSA	body surface area
BTK	Bruton's tyrosine kinase
BUN	blood urea nitrogen
CAPRA	Cancer of the Prostate Risk Assessment
CBC	complete blood cell (count)
CHR	Committee on Human Research (UCSF IRB)
CpG	cytosine-phosphate-guanine
CNS	central nervous system
CR	complete response
CRC	Clinical Research Coordinator
CrCl	creatinine clearance
CRF	case report form
CSF	cerebral spinal fluid
CT	computerized tomography
CTCAE	Common Terminology Criteria for Adverse Events
CTEP	Cancer Therapy Evaluation Program
CTL	cytotoxic T lymphocyte
CTLA-4	cytotoxic T-lymphocyte-associated protein 4
CTMS	Clinical Trial Management System
CYP	cytochrome P450
DFS	disease-free survival
DL	dose level
DLBCL	diffuse large B-cell lymphoma
DLT	dose limiting toxicity
D2	dopamine receptor D2
DSMC	Data and Safety Monitoring Committee
DSMP	Data and Safety Monitoring Plan
EC ₅₀	median effective concentration
ECG	Electrocardiogram
ECOG	Eastern Cooperative Oncology Group
FCBP	female of childbearing potential
FDA	Food and Drug Administration
FIH	first-in-human
FL	follicular lymphoma
GCP	Good Clinical Practice
g/dL	gram per deciliter
Hb	Hemoglobin
HBcAb	Hepatitis B core antibody
HBeAg	Hepatitis B "e" antigen
HBsAb	Hepatitis B surface antibody
HBsAg	Hepatitis B surface antigen

List of Abbreviations

HBV	hepatitis B virus
HCT	Hematocrit
HCV	hepatitis C virus
HDFCCC	Helen Diller Family Comprehensive Cancer Center
HED	human equivalent dose
HGB	Hemoglobin
HIV	human immunodeficiency virus
IB	investigator's brochure
IC ₅₀	concentration that inhibits a process by 50%

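### The grade 3 leukocytosis line in Section 6.3 is triggered and released by the neutrophil count, so a lymphocyte-driven count above 100,000/mm³ would not start its suggested admission and leukostasis watch

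*Combined protocol and SAP*

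**What the plan says.** The Section 6.3 table has a row headed "Leukocytosis (common"), a label that the table's frequency note explains as "anticipated ≥1% and <10"%. The grade 3 line of that row opens "Grade 3 (ANC >100,000/mm"³). Its management text is "Admit patient for close monitoring including CBC and signs and symptoms of leukostasis", followed by "Hold ibrutinib until ANC normalizes, at which time resume ibrutinib at 50% of the starting dose". The grade 4 line depends on clinical signs of leukostasis, whatever the cell type, and stops the drug.

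The List of Abbreviations gives ANC as "absolute neutrophil count" and lists WBC as a separate entry. Section 3.3.1 sets separate eligibility limits for the two, and Section 6.1.3 takes the WBC count before surgery into the safety analysis.

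The table column is headed "Dose Modification and Suggestions for Management", and Section 6.2 leaves the plan for each patient to clinical judgment.

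**The concern.** The row names a rise in white cells but measures only neutrophils. The count rise that the protocol itself links to ibrutinib is in lymphocytes: Section 1.2.1.3 describes it in subjects with CLL, and Section 6.1.4 says lymphocytosis may be an on-target effect. A lymphocyte rise does not move the ANC.

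Both ends of the rule are affected. A very high lymphocyte-driven count does not start the line. If a clinician applied the line anyway, the release condition could already be met on day one, because a normal ANC says nothing about whether the high count has resolved.

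At stake is the one written prompt to admit a man and watch for leukostasis before it shows clinically. No error rate, power figure or DLT count is involved.

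**Working it through.** The plan states no figure on this point that could be reproduced. The check compares the sections and then adds short arithmetic.

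**1. Is ANC used loosely for WBC?** No. The abbreviation list separates them, and Section 3.3.1 requires WBC above 2,500 and ANC above 1,500 cells/mm³ as two criteria. The Neutropenia and Febrile neutropenia rows of the same table use ANC in its proper sense. The abbreviation appears twice in the leukocytosis line, once in the trigger and once in the release.

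**2. Does a lymphocyte-driven count meet the trigger?** ANC = WBC × neutrophil share. The counts below are assumed, for illustration only.

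- WBC 110,000 = lymphocytes 100,000 + neutrophils 5,000 + other cells 5,000. ANC ÷ trigger = 5,000 ÷ 100,000 = 5%. Not met.
- WBC 120,000 with a neutrophil share of 5% to 40%: ANC = 120,000 × 0.05 = 6,000 to 120,000 × 0.40 = 48,000. Not met.
- At WBC 120,000 the trigger is met only if the neutrophil share exceeds 100,000 ÷ 120,000 = 83%.

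ANC cannot exceed WBC, so a WBC trigger at 100,000 would capture every case that the present line captures, and the lymphocyte-driven ones as well.

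**3. Does another rule start the same action?**

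| Rule | What it does | Admission or leukostasis watch before symptoms? |
|---|---|---|
| Section 6.2, attributed grade 3 toxicity | Hold; may resume at 50% dose | No |
| Section 6.3, other ibrutinib-related AEs, grade 3 | Hold, then 50% dose | No |
| Section 6.3, leukocytosis grade 4 | Discontinue, supportive care | No; needs clinical leukostasis |
| Section 6.1.4, lymphocytosis exclusion | Removes symptom-free lymphocytosis from DLT | No; concerns DLT counting only |

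None does.

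**4. How many men could be affected?** The documents give no rate for counts above 100,000. The only figure is the row's frequency label, p from 0.01 to under 0.10, with no grade named. For the 24 men planned at the phase 2 dose:

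- Expected number with any leukocytosis: 24 × 0.01 = 0.24 to under 24 × 0.10 = 2.4.
- Chance of at least one: 1 − 0.99²⁴ = 21% to under 1 − 0.90²⁴ = 92%.

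These figures cover leukocytosis of any grade and any cell type. They are a ceiling for the row and do not estimate the grade 3, lymphocyte-driven case.

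**The case against.** The strongest reply is that this is a wording slip with almost no practical reach. The lymphocyte rise is described only in CLL, where it is presumed to come from CLL cells leaving tissue. Exclusion 17 in Section 3.3.2 bars concurrent active malignancy other than non-melanoma skin cancer, so men with active CLL should not be enrolled. Section 6.3 lists leukocytosis among the effects to monitor without restricting it to neutrophils, and blood counts during treatment are about a week apart. Section 6.2 still holds the drug for an attributed grade 3 toxicity. The table offers suggestions, and no clinician facing such a count would be kept from admitting the man by an abbreviation.

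All of this stands as an argument about weight, and it puts the point at the bottom of the minor range. It does not make the line correct: none of these provisions contains the admission and watch that the line was written to prompt. On Days 8 and 22 the contact is by telephone and the count may come from a local laboratory. Staff then have numbers without an examination, which is when a correct written threshold helps most.

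A second reply is that a WBC trigger would make a symptom-free, possibly on-target lymphocytosis a reason to interrupt and halve the dose. That is a real cost of the change. However, Section 6.2 already requires the hold and limits resumption to half dose when the event is an attributed grade 3 toxicity.

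**Conclusion.** The concern holds as a minor error in the text. The grade 3 leukocytosis line uses the wrong measure for both trigger and release, and a lymphocyte-driven count above 100,000/mm³ would not start its suggested admission and leukostasis watch.

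The conclusion rests on reading ANC as the protocol defines it. The size is small: such counts are likely very rare in men with localized prostate cancer, the documents do not allow a number to be given, and the scheduled counts would reveal the rise. Nothing is claimed about how the event would be graded, because Section 9.2 applies modified criteria to hematologic adverse events without setting them out there. The sample size, the DLT rule and the primary analysis are unaffected.

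**What to change.** In the Leukocytosis row of Section 6.3, replace ANC with total WBC in the grade 3 trigger and in the condition that ends the hold. Add a note that lymphocytosis without clinical symptoms remains excluded from DLT under Section 6.1.4, so DLT counting does not change.

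The cost is a wording change in one table row. A CBC with differential is already scheduled at seven time points in Section 8.2: screening, Days 1, 8, 15, 22 and 29, and follow-up. The downside falls on a rare man with a very high count and no symptoms: an admission, a hold and a restart at half dose. The table notes also require discontinuation in this case: "If a patient requires a dose interruption of >14 days due to a study drug related toxicity". That limit is half of the 28-day course. If the sponsor wishes to avoid the dosing consequence, a narrower change would tie only the admission and leukostasis watch to total WBC and leave dosing to Section 6.2.
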